2.3. Definitions

Laboratory panel: the set of ordered laboratory tests ordered by the physician. This panel consists of a series of laboratory tests ordered for one or more indication at one time by a single physician.

Indication: the reason for ordering a series of laboratory tests. A single panel may have more than one indication and sometimes a single test can be ordered for more than one indication.

Study indication: one of the indications included in the study protocol.

Order sets: a set of laboratory tests that are suggested when an indication is selected.

[figure not shown]

Figure 1: Graphic representation of the relationship between the different clusters and items.

3. Study methods

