4. KCELABGP_COM

6.1.1.KCELABGP_LAB

The KCELABGP_LAB database contains the data collected through the ambulatory laboratories. This database contains several tables, each containing data from the same data collections. The tables included in the KCELABGP_LAB database are TU_KCELABGP_LAB, TU_KCELABGP_LAB_INDICATN, TU_KCELABGP_LAB_TST, TU_KCELABGP_LAB_ORD_SETS, TU_KCELABGP_LAB2 and TU_KCELABGP_LAB2_LAB_TST.

TU_KCELABGP_LAB

This table contains data on each individual laboratory panel linked to an individual patient. The table includes information on date of birth, sex, reimbursement codes, physician, date of the laboratory test

panel, date of death (if applicable) and total cost of the laboratory test panel. Each row in this table represents a unique laboratory test panel and a single patient may be represented more than once.

TU_KCELABGP_LAB_INDICATN

This table contains data on the indications for each laboratory test panel. It includes data on the selected indications and the additional information provided by the physician when code 99 was used. Code 99 implied that the physicians reported that an indication was applicable outside of the 17 study indications. The exact nature of this indication was included in a free text field of the CPOE. Each row represents a unique indication. Since many laboratory test panels had more than one indication, most panels are represented multiple times.

TU_KCELABGP_LAB_LAB_TST

This table contains data on all ordered laboratory tests. Data on the laboratory test (either a Logical Observation Identifiers Name and Codes (LOINC) code or a Medidoc code), result of the test, upper limit, lower limit are included. Data on whether the result represents a normal or abnormal value is also included. The laboratory test results can be numeric or alphanumeric so that a wide variety of results are possible. Each row in the table represents a unique test. Each panel is represented multiple times as is each patient.

TU_KCELABGP_LAB_ORD_SETS

This table contains data on the selected order sets. For each possible indication, multiple order sets were developed. For instance, for the indication 'hypertension' an order set was developed for the diagnosis of hypertension, for the follow-up of hypertension and so on. This table includes more detailed information on the exact order set that was selected with respect to the indication.

TU_KCELABGP_LAB2 and TU_KCELABGP_LAB2_LAB_TST

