Alongside the 17 indications included in the study, physicians had the possibility to add other indications. These indications are included in the database as "99" and a free text field allowed physicians to specify the nature of these indications. In some situations, the free text clearly shows that one or more of the additional indications is in fact one of the study indications. Hence, all references to one or more of the study indications will be recoded from "99" to one of the study indications. Where necessary, a second assessment of the indication will be sought, and if there is any doubt about the indication, it will not be recoded.

6.3.3.KCELABGP_GP

This database contains records that were valid in the past, as well as currently valid records that replace earlier records. Only the currently valid records will be included for further analysis. Furthermore, we will only analyze the data that comes from eForms that can be linked to a corresponding lab panel (see 46.2).

The protocol of this trial states that all new diagnoses made within a period of six months after the laboratory date will be analyzed. Therefore, all diagnoses with a start date before or 6 months after the laboratory date will be excluded. Also diagnoses with unclear labels or where the description clearly indicates that they are not diagnoses but rather treatments or examination will be excluded.

The content of the diagnoses in this table is represented by an ICPC-2 code[8], an ICD-10 code, a free text label or a combination of these three. Since ICPC-2 is the most widely used international classification for systematically recording and analyzing primary care information¹, we will use these codes for further analysis. Therefore, we will complete missing ICPC-2 codes by converting ICD-10 codes or free text labels to their corresponding ICPC-2 code, using the Dutch ICPC-2 and ICPC-ICD10-tables, as well as the Belgian Bilingual Biclassified Thesaurus (3BT), provided by eHealth for all Belgian EHR developers, as conversion tables. All remaining free text labels will be manually recoded to an ICPC-2 code. This will result in an additional tailor-made conversion table named 'DIAG_FREETXT'.

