7.1. Pre-analysis checks

Prior to database lock, based on the data cleaning actions, a final set of patients who meet the inclusion criteria and for whom tests were ordered for one or more of the study indications will be defined. When the last data collection has been completed and when completed data collections forms for at least 85% of the included patients have been imported into the database, a pre-analysis report will be drafted. This document will report on the status of all databases, including:

- Overview of missing forms per physician
- Overview of missing forms per laboratory
- Overview of missing forms per EHR system

If certain outstanding forms are deemed critical for database lock, the investigators responsible for these forms will be contacted to resolve these issues. The outstanding issues and the timeline for these issues will be reported on the pre-analysis report and signed off by the Chief Investigator, Trial Coordinator and Chief Statistician.

Upon resolution of outstanding actions, the database can be locked.

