10.1. Outcome definitions

10.1.1. Primary outcome appropriateness

We chose to use a restrictive definition to appropriateness as defined by Zhi et al.[9] Appropriateness is therefore directly related to the suggested tests in the study intervention. Tests not included in the study order sets are considered inappropriate. The order sets vary according to specific situations. For example, in some cases, an order set for initial diagnosis was used, but in other situations an order set for follow-up was used. In the composite outcome appropriateness, all tests included in the order sets will be considered appropriate for a given indication. Below, we specify exactly which tests will be considered appropriate for each study indication. Tests in red are considered inappropriate when they are absent from the panel for the given indication. Tests for underutilization were identified through the National Institute for Health and Care Excellence (NICE) quality standards.[10] Those tests considered an essential part of any type of laboratory investigation (diagnosis, follow-up, etc.) for one of the study indications were considered inappropriate when not ordered. We identified tests for inappropriate under-utilization for the indications diabetes mellitus, chronic kidney disease, rheumatoid arthritis and thyroid disease.

| Study indication | Test | Code (LOINC) |
|--------------------------------|-----------------------------|--------------|
| Cardiovascular risk assessment | Cholesterol total | 2093-3 |
| Cardiovascular risk assessment | Cholesterol HDL | 2085-9 |
| Cardiovascular risk assessment | Cholesterol total/HDL ratio | 32309-7 |
| Cardiovascular risk assessment | Cholesterol total/HDL ratio | 9830-1 |
| Cardiovascular risk assessment | Triglycerides | 2571-8 |
| Cardiovascular risk assessment | Cholesterol non-HDL | 43396-1 |
| Cardiovascular risk assessment | Cholesterol LDL calc | 13457-7 |
| Cardiovascular risk assessment | Glucose post meal | 16915-1 |
| Cardiovascular risk assessment | Glucose 2h post meal | 6689-4 |
| Cardiovascular risk assessment | Glucose fasting | 1558-6 |
| Cardiovascular risk assessment | Glucose serum | 2345-7 |
| Cardiovascular risk assessment | GGT | 2324-2 |
| Cardiovascular risk assessment | ALT (GPT) | 1742-6 |

Table 2: Appropriate tests for the indication 'cardiovascular risk assessment'.

| Study indication | Test | Code (LOINC) |
|------------------|----------------------------------|--------------|

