10.2. Analysis methods

10.2.1. Primary outcome analysis

Appropriateness

For the definition of the primary outcome, three numbers are relevant: (a) the number of requested tests which are appropriate, (b) the number of requested tests which are inappropriate and (c) the number of inappropriately not-requested tests. As indicated in section 5b, the latter number is only relevant for diabetes mellitus, chronic kidney disease, rheumatoid arthritis and thyroid disease. Per patient, aggregated over panels if multiple panels are available, the primary outcome is defined by the ratio $(a)/(a+b+c)$. We will refer to this ratio as the proportion of appropriate tests in the remainder.

To assess differences between the allocated groups in the proportion appropriate tests, a logistic generalized estimating equation (GEE) model will be used: of interest are the marginal proportions, not the proportions on patient, physician or PCP level.

The logistic GEE model will include the allocated group and laboratory as factors and PCP as the clustering variable. The effect of the intervention will be expressed as the difference in proportions and will be presented together with its associated 95% confidence interval. The proportion of appropriate tests in the two allocated groups will also be estimated from the GEE model and presented with their 95% confidence intervals.

Appropriateness for the composite of all study tests will be compared between intervention and control groups. Furthermore, an additional analysis will be performed that only includes patients who have no indications in addition to the 17 study indications. This additional analysis will correct for an overestimation of inappropriate tests when more than one indication is selected, including indications not under evaluation. These tests would be considered inappropriate even though they could be appropriate according to one of the other indications not being evaluated.

The analyses will be performed on all patients from all physicians according to their allocated group.

Appropriateness for each study indication separately will be performed as a secondary analysis. In this analysis we will include the number of additional indications for the panel as a factor in the analysis.

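### The SAP tables that score the primary outcome do not match the supplied protocol: obesity has no test list, and the general check-up list lacks TSH

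*SAP*

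**What the plan says.** Protocol 5.2 selects 17 indications and lists them in Table 3. Obesity is number 16, and diarrhea is a single entry. Protocol 5.3 says that 17 order sets will be introduced and evaluated. Protocol 5.2 also describes the general check-up set as cardiovascular risk tests plus, for elderly patients, TSH.

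The SAP ties its own term to the protocol: "Study indication: one of the indications included in the study protocol" (SAP 2.3). For scoring, SAP 10.1.1 gives two rules. One is restrictive: "Tests not included in the study order sets are considered inappropriate". The other pools the variants of each set: "all tests included in the order sets will be considered appropriate for a given indication". It then presents Tables 2-17 as complete: "Below, we specify exactly which tests will be considered appropriate for each study indication".

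Other steps depend on what counts as a study indication:

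- The final patient set consists of those "for whom tests were ordered for one or more of the study indications will be defined" (SAP 7.1).
- SAP 6.1.1 describes the residual code: "Code 99 implied that the physicians reported that an indication was applicable outside of the 17 study indications".
- In free text entered under that code, "all references to one or more of the study indications will be recoded from" 99 to the study indication concerned (SAP 6.3.2).
- For appropriateness, "an additional analysis will be performed that only includes patients who have no indications in addition to the 17 study indications" (SAP 10.2.1). SAP 10.2.2 plans the same restriction for diagnostic error.

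**The concern.** Tables 2-17 decide which requested tests count as appropriate (a) and which as inappropriate (b) in the primary outcome a/(a+b+c). A study indication without a list leaves part of that outcome undefined, and two programmers following the SAP could score the same panel differently. The handling of obesity also determines who enters the restricted analyses of appropriateness and diagnostic error, and whether the per-indication analysis can be run for obesity at all.

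The TSH gap is of another kind. If the tool proposed TSH in the check-up set, Table 6 would count a test as inappropriate because the physician followed the intervention. What is at stake is a fixed, reproducible definition of the primary outcome more than the direction of the result.

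**Working it through.** **Count of indications.** Protocol Table 3 has 17 entries, which agrees with the 17 stated in protocol 5.2. SAP Tables 2-17 are 16 tables. Table 12 carries two indications (acute coronary syndrome and lung embolism), so there are 17 labels. Mapped one to one, acute diarrhea (Table 16) and chronic diarrhea (Table 17) both belong to the protocol's single diarrhea entry. The labels therefore cover 16 of the 17 protocol indications, and the one missing is obesity. Cardiovascular disease has also been relabelled cardiovascular risk assessment. The table numbers run without a break, so this is not a loss in text extraction.

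**Check-up list.** Table 6 has 11 codes, 7 lipid and 4 glucose. Neither TSH code used elsewhere (3016-3, 11580-8) is among them. TSH is listed for hypertension, fatigue, anemia and thyroid disease (Tables 3, 5, 8 and 14).

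**Three treatments of an obesity-only panel.**

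1. Obesity is a study indication (SAP 2.3), so the patient is eligible (SAP 7.1), but no test is listed. The panel scores 0.
2. Obesity had an order set (protocol 5.3), and the SAP rules refer to order sets, so the panel is scored against that deployed set.
3. The SAP's own 17 labels define the indications, so obesity is coded 99. Obesity-only patients leave the patient set, and patients with obesity plus a listed indication leave the restricted analyses.

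**Size, obesity, treatment 1.** Let s be the share of obesity-only patients, equal in both arms. The documents give no value for s. The planned 70% and 80% become 70(1-s)% and 80(1-s)%.

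- s = 2%: 78.4 - 68.6 = 9.8 points
- s = 5%: 76.0 - 66.5 = 9.5 points

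Under treatment 3 the 10 points are unchanged. Unequal shares would matter more. With 2% in control and 5% in intervention, 76.0 - 68.6 = 7.4 points. With 3% in control and 1% in intervention, 79.2 - 67.9 = 11.3 points. Nothing in the documents suggests such a difference.

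**Size, TSH.** Bias = share of affected patients x difference in TSH use between arms / tests per patient.

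- Check-up is one of five indications making up almost 40% of all panels (protocol 5.2). An equal split (assumed) gives 40%/5 = 8% of all panels. That is 8% of study panels if the study indications cover all panels, and 8%/0.40 = 20% if they cover only those five.
- Half are assumed to have no other indication that lists TSH: 4% to 10%.
- Elderly patients are assumed to be 20% to 50% of check-ups.
- TSH use in them is assumed 50 points higher in the intervention arm.
- Tests per panel: 14.2 to 14.61 at the three laboratories (protocol 4); 14.3 is used.

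Lower end: 0.04 x 0.2 x 0.50/14.3 = 0.03 points. Upper end: 0.10 x 0.5 x 0.50/14.3 = 0.17 points, against the intervention. Equal use gives 0. If control use were 10 points higher in elderly patients, the upper end is 0.10 x 0.5 x 0.10/14.3 = 0.03 points in favour of the intervention.

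**Worst combination with equal obesity shares.** 0.95 x (10 - 0.17) = 9.3 points.

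**The case against.** The strongest reply is that the supplied protocol may not be the one the SAP uses. The SAP builds on protocol version 3.6, and the supplied text differs from the SAP on intervention length (three versus six months) and on stratification (CPOE experience versus laboratory). Protocol 5.2 refers to Appendix 2 for the full order sets, which is not in the supplied text, and protocol 8.7 provides for tailoring the sets. Obesity or the check-up TSH may have been dropped properly. If obesity was not on the CPOE menu, 17 labels with obesity entered as 99 would be coherent. This stands, and it limits the point to the mismatch and the missing statement.

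A second reply also stands. SAP 7.1 requires the patient set to be defined before lock, and SAP 8 unblinds the study team only after lock. A reader might infer that obesity patients could be taken in or out with knowledge of the allocation; the documents do not support that. What stays open is mainly the scoring of retained panels and the membership of the restricted analyses.

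A third reply concerns size. A reader might apply the 50-point TSH gap to all check-up patients and divide by the 5 study tests of the sample-size section, obtaining 0.10 x 0.50/5 = 1.0 point and a worst combination of 0.95 x 9.0 = 8.55. Protocol 5.2 has TSH only for elderly patients, and the SAP denominator counts all requested tests, so those figures are too large. Grouping of tests under SAP 6.4.2 may bring the count below 14.3, but even at 5 tests the elderly-only upper end is 0.10 x 0.5 x 0.50/5 = 0.5 points.

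None of this supplies the missing sentence. The SAP claims exact lists for each study indication and does not deliver them for the protocol it points to, so far as that protocol can be seen.

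**Conclusion.** The mismatch is certain for the supplied texts: obesity has no list, and Table 6 has no TSH. The SAP leaves three treatments of obesity panels open. If TSH was deployed in the check-up set, Table 6 contradicts the SAP's pooling rule; that condition cannot be checked here, and protocol 5.1 (Figure 9) also mentions optional tests, so TSH may not have been pre-selected.

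The effect is probably small and mostly attenuating: at most about 0.2 points for TSH, and 10 points reduced to about 9.3 in the worst combination. These figures rest on assumed shares, on equal obesity shares in the two arms, and on the harshest treatment of obesity. The primary conclusion would probably survive.

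Two stronger readings are tempting. One is that the sponsor dropped an indication without recording it. A later protocol version or tailoring could account for that, so the documents do not show it. The other is that obesity panels will score 0, but that is only one of three treatments the text allows. The point should be fixed because it concerns the definition of the primary outcome and costs little.

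**What to change.** Before the laboratory database is locked (SAP 7.2 locks it ahead of the final data collection) and before unblinding:

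- Reconcile Tables 2-17 with Appendix 2 of the protocol version in force and with the order sets deployed in both CPOEs, including the diarrhea split and the cardiovascular label.
- Either add the obesity list, or state that obesity was dropped and how its panels are handled in the code-99 recoding (SAP 6.3.2), the patient set (SAP 7.1) and the restricted analyses (SAP 10.2.1 and 10.2.2).
- Make Table 6 agree with the deployed check-up set, or record the date of and reason for the change from protocol 5.2.
- Run a programmed comparison of the scoring lists with the deployed definitions.

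The cost is a few table rows or two sentences, one comparison and one short program. No new patient data are needed. Which tests are clinically right is not at issue; the passages must be reconciled.
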